 - b. Relationships between clinical and laboratory values will be evaluated in longitudinal mixed effect models. We will develop models that capture the combined frequency and severity of disease manifestations while accounting for age of onset, protoporphyria subtype (EPP and XLP), and genotype. A sample size of 150 (assuming a minimum of 3 follows ups per patient, a correlation of 0.7 among outcomes over time from the same subject, a variance of outcome equal to 1 and a compound symmetric covariance structure) yields 91% power to detect a moderate interaction ($\beta=0.4$) between time and an associated factor of interest.
 - c. A severity score based on predictive demographic and clinical characteristics will be developed
 - d. After 100 participants are enrolled, the mean score of the Hospital Anxiety and Depression Scale (HADS) will be computed and compared to the general population value. A sample size of 100 yields 90% power to detect a 20% difference in HAD-scale between the general population and our sample at the .05 significance level. The illness Perception Questionnaire and EPP/XLP-specific questionnaire will also be scored.
 - e. During this interim look at $n=100$, we will re-evaluate the estimates used in our initial power calculation that yielded a sample size of 150 and determine whether the study needs to be extended beyond this point to examine correlations of QoL scale scores with clinical severity and genotypes

Sponsors (federal, state, foundation and industry support): National institutes of Health (NIH)

1. Protocol Overview

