Erythropoietic protoporphyria (EPP) is the third most common porphyria, with an incidence of 2 to 5 per 1,000,000, and the most common in children. Most cases are due to the markedly reduced activity of the enzyme, ferrochelatase (20-30% of normal). The inheritance of EPP follows an autosomal recessive pattern. In about 95% of EPP cases, the individual has a severe mutation of the ferrochelatase (*FECH*) gene inherited from one parent, and a common genetic variation of the same gene, inherited from the other parent. This common genetic variation causes reduced production of the enzyme, but does not cause disease in the absence of a severe mutation. The frequency of this common genetic variation in the *FECH* gene varies by population, such that it is present in about 10% of Caucasians, 43% of Japanese, 31% of Southeast Asians, and 1 to 3% in Blacks. Alternatively, in about 5% of EPP cases, two severe *FECH* gene mutations, one inherited from each parent, are found in the same patient,

A second type of erythropoietic protoporphyria, X-linked Protoporphyrria (XLP) is an X-linked porphyria caused by a mutation in the last exon of the δ -aminolevulinic acid synthase-2 (*ALAS2*) gene. The *ALAS2* gene mutation results in a “gain of function” and results in increased stability and/or activity of this enzyme. Therefore, more protoporphyrin than is needed for hemoglobin synthesis is produced by the bone marrow. In all cases of EPP, protoporphyrin accumulates in the marrow and is transported to the skin in the plasma and red blood cells, causing photosensitivity. Protoporphyrin is not excreted by the kidneys, but is taken up by the liver and excreted in bile. It can reduce bile flow and damage the liver.

Photosensitivity in both EPP and XLP begins in early childhood, and can be difficult to diagnose, since there is usually no blistering and little scarring. Photosensitivity is typically acute – appearing soon after exposure to sunlight – rather than chronic. It is also painful, and may be accompanied by swelling of the skin. These symptoms greatly impair quality of life and limit employment opportunities and life style. Patients are sensitive to sunlight that passes through window glass (long wave ultraviolet light). Large

amounts of protoporphyrin in bile can form stones rich in this porphyrin. Severe liver complications are difficult to treat and sometimes require liver transplantation.

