- 1) Characterizing EPP and XLP Illness Perception via the Illness Perception Questionnaire, dermatology-specific QOL via the Dermatology Life Quality Index and EPP-specific QOL via the EPP/XLP specific questionnaire. The mean and standard deviation of each scale in our sample will be assessed.
- 2) Scores for all four QOL assessments will be analyzed; FECH and ALAS 2 mutations correlations will be sought with clinical parameters, disease severity score and genotypes.

Secondary analyses will inform whether a study extending beyond 100 patients will be needed to examine correlations of QOL scale scores with clinical severity and genotypes.

6. B Power Calculation

For the proposed analyses, the statistical powers are of two sided tests, with 0.05 level of significance.

Linear mixed effects model: We may assume, for example, that 150 participants will have at least 3 follow up visits per subject. Taking into account the correlation among outcomes over time from the same subject, the main interest is in determining whether the regression coefficient of the interaction between time and covariate of interest is zero or not. Using GPower 3.0, Table 6-1 shows the results when the variance of outcome is equal to 1, where ρ and β denote correlation among repeated outcome measures and effect size of the interaction, respectively. In this calculation, we assume compound symmetry for the covariance structure of repeated outcome measures from the same subject and the same number of subjects in each group with/without a potential factor of interest. The study is certain to detect moderate ($B \geq 0.4$) differences in the analysis.

Table 6-1. Power calculation for linear mixed effects model based on the most common types of porphyria (AIP and PCT)

Sample size	ρ	B for time x factor of interest	Power
150	0.5	0.3	0.45
		0.4	0.72
		0.6	>0.99
	0.7	0.3	0.67
		0.4	0.91
		0.6	>0.99

7. Data Management

All study data will be collected via systems created in collaboration with the RDCRN Data Management and Coordinating Center and will comply with all applicable guidelines regarding patient confidentiality and data integrity.

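### Section 6.B calls detection of B ≥ 0.4 certain, but Table 6-1 gives power of 0.72 or 0.91 at B = 0.4, and the synopsis reports only the higher figure

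*Combined protocol and SAP*

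**What the plan says.** Section 6.B powers the test of a time-by-factor interaction in a linear mixed model. It uses 150 participants, at least three follow-up visits each, outcome variance 1, compound symmetry and a two-sided 0.05 level. It also assumes "the same number of subjects in each group with/without a potential factor of interest". Its conclusion is that "The study is certain to detect moderate" differences, defined there as B of at least 0.4.

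Table 6-1 follows immediately. Its caption reads "Power calculation for linear mixed effects model based on the most common types of porphyria (AIP and PCT"). The printed power is:

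| Correlation | B = 0.3 | B = 0.4 | B = 0.6 |
|---|---|---|---|
| 0.5 | 0.45 | 0.72 | >0.99 |
| 0.7 | 0.67 | 0.91 | >0.99 |

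Item b of the analysis plan in the synopsis says that a sample of 150 "yields 91% power to detect a moderate interaction" at β = 0.4, "assuming a minimum of 3 follows ups per patient, a correlation of 0.7 among outcomes over time from the same subject", with variance 1 and compound symmetry. Equal groups are not among the listed conditions, and the result for a correlation of 0.5 is not given. Item e plans, at n = 100, to "re-evaluate the estimates used in our initial power calculation that yielded a sample size of 150".

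**The concern.** The sentence in 6.B is the only conclusion the section draws from the table, and the table contradicts it. Power of 0.72 is not certainty, and neither is 0.91. Item e of the synopsis ties the sample size of 150 to an initial power calculation, and item b gives this mixed-model calculation for that number. A reader who takes 6.B at its word could therefore treat a null interaction as evidence that no moderate effect exists.

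Two further points affect how the figures are read. The synopsis gives only the more favourable of the two correlation scenarios and omits a condition on which the figure depends. The caption attributes the calculation to two porphyrias outside this protocol, and nothing says whether the correlation, variance and effect size were chosen with EPP and XLP in mind.

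**Working it through.** **Text against table.** This step needs no modelling. At B = 0.4, the lower end of the range called certain, the chance of missing a true effect is 1 − 0.72 = 0.28 at correlation 0.5 and 1 − 0.91 = 0.09 at correlation 0.7. Among the tabulated effects, >0.99 appears only at B = 0.6.

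**Reproducing the B = 0.4 cells.** Section 6.B names GPower 3.0 but does not say how B was converted to that program's effect size, so the conversion here is inferred. Take a within-between interaction F test with m = 3 measurements, group shares p = q = 0.5, and a group difference of B at one time point:

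- f² = p·q·B²·(m − 1)/m² = 0.25 × 0.16 × 2/9 = 0.00889
- λ = f²·N·m/(1 − ρ) = 0.00889 × 450/(1 − ρ) = 8.0 at ρ = 0.5 and 13.3 at ρ = 0.7
- degrees of freedom: m − 1 = 2 and (N − 2)(m − 1) = 296
- power: 0.713 and 0.912, against 0.72 and 0.91 printed

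With m = 4 the results are 0.707 and 0.914. The B = 0.3 cells come out at 0.456 and 0.683 with m = 3, against 0.45 and 0.67 printed. The table is therefore plausible at B = 0.3 and 0.4.

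**How large B must be for near-certainty.** By a normal approximation anchored on the B = 0.4 cells, the standardized effect is d = 1.96 + z(power). This gives 1.96 + 0.58 = 2.54 at ρ = 0.5 and 1.96 + 1.34 = 3.30 at ρ = 0.7. For 99% power, d must be 1.96 + 2.33 = 4.29, so B = 0.4 × 4.29/2.54 ≈ 0.67 at ρ = 0.5 and 0.4 × 4.29/3.30 ≈ 0.52 at ρ = 0.7.

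**The >0.99 entry at ρ = 0.5, B = 0.6.** Moving from B = 0.4 to 0.6 multiplies d by 1.5 and λ by 2.25. Anchored on 0.72:

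| Form of test | Value at B = 0.4 | Value at B = 0.6 | Power at B = 0.6 |
|---|---|---|---|
| Normal, 1 df | d = 2.54 | d = 3.81 | 0.968 |
| F, 2 and 296 df | λ = 8.12 | λ = 18.3 | 0.975 |
| F, 3 and 444 df | λ = 9.25 | λ = 20.8 | 0.979 |

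None exceeds 0.99. At ρ = 0.7 the same steps give about 0.999, which agrees with the print.

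**Unequal groups.** The noncentrality scales with 4p(1 − p), so d scales with its square root. At 40:60 the factor is 0.96, and power at B = 0.4 is about 0.70 (ρ = 0.5) and 0.90 (ρ = 0.7). At 30:70 it is 0.84, and power is about 0.65 and 0.86 by the normal form, or 0.63 and 0.86 by the F form with m = 3. These splits are assumptions chosen for illustration.

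**The case against.** The strongest reply is that this is loose wording with little effect. The synopsis says 91%, not certain, and 6.B prints 0.72 and 0.91 right under the sentence. The equal-group assumption is stated in 6.B, a synopsis has to condense, and power barely moves at 40:60. Section 8.A expects equal numbers of males and females, so at least one plausible factor meets the assumption. The caption looks like a carry-over, since the table uses this study's 150 and generic inputs.

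Most of this stands, and it limits the point to a correction of wording and disclosure. It does not rescue the sentence, because no reading of certainty fits 0.72. Nor does condensing explain why the synopsis gives only the higher of two results.

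Three stronger readings should be resisted.

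- A reader might infer that the genotype analyses have very low power. The Background says "In about 95% of EPP cases, the individual has a severe mutation of the ferrochelatase" gene plus a common variant, with about 5% carrying two severe mutations. At a 95:5 split, scaling from the table would give roughly 0.2 to 0.3 at B = 0.4. But the plan claims no power for that contrast and does not define how genotype will be coded. The scaled figure also depends on which table cell is used as anchor.
- A reader might infer that Table 6-1 is miscalculated at B = 0.6. The effect-size form is not given, so the mismatch is a reason to recheck, not proof of an error.
- A reader might infer that the caption shows the inputs do not apply to EPP and XLP. It shows only that their source is unclear.

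**Conclusion.** The statement in 6.B is wrong as written. On the plan's own table, power at B = 0.4 is 72% to 91%, leaving a 28% or 9% chance of missing a true effect, and this holds for a factor that splits the 150 participants equally. Synopsis item b is incomplete because it omits the equal-group condition and the lower figure. The contradiction rests on the text and table alone. Only the B = 0.6 recheck and the unequal-group figures depend on an inferred form of test, and the latter serve only as a caution that power falls as the split becomes uneven.

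The point does not call the sample size into question. The HADS comparison has its own power statement and is untouched. The decision in item e on whether the study must be "extended beyond this point to examine correlations of QoL scale scores with clinical severity and genotypes" concerns a different analysis from this interaction test.

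**What to change.** 1. In 6.B, replace the sentence claiming certainty with: *For a factor that splits the 150 participants equally, power at B = 0.4 is 72% (ρ = 0.5) to 91% (ρ = 0.7).* A clause noting that power is lower for unequal splits would be a sensible caution.
2. Recheck the >0.99 entry at ρ = 0.5, B = 0.6 from the original program settings before citing it in any text.
3. In synopsis item b, add the equal-group condition and the 72% result at ρ = 0.5.
4. Confirm where the correlation, variance and effect-size inputs came from. Then either correct the caption to EPP and XLP or state that the inputs were carried over from AIP and PCT.

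The cost is a few sentences and one check of the calculation. The sample size, data collection and HADS analysis do not change.
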